### 9.3.2 Exclusion Criteria

Subjects who meet any of the following criteria will be excluded from this study:

1. Subjects with CNS metastases are not eligible, unless they have completed local therapy and have discontinued the use of corticosteroids for this indication for at least 4 weeks before starting treatment in this study. Any signs (eg, radiologic) or symptoms of brain metastases must be stable for at least 4 weeks before starting study treatment.
2. Prior exposure to lenvatinib
3. Subjects who have not recovered from toxicities to  $\leq$  Grade 1 as a result of prior anticancer therapy, except alopecia
4. Major surgery within 3 weeks prior to the first dose of lenvatinib
5. Subjects having  $\geq 2+$  proteinuria on urine dipstick testing will undergo a 24-hour urine collection for quantitative assessment of proteinuria. Subjects with a urine protein  $\geq 1$  g/24 hours will be ineligible.
6. Uncontrollable diabetes as defined by fasting glucose  $> 1.5 \times \text{ULN}$
7. Fasting total cholesterol  $> 7.75$  mmol/L ( $> 300$  mg/dL)
8. Fasting triglycerides  $> 2.5 \times \text{ULN}$
9. Gastrointestinal malabsorption, a history of gastroenterostomy, inability of oral administration, or any other condition that might affect the absorption of lenvatinib and/or everolimus
10. Significant cardiovascular impairment:
  - a. Congestive heart failure than New York Heart Association (NYHA) Class II within 6 months of the first dose of study drug
  - b. Unstable angina, myocardial infarction or stroke within 6 months of the first dose of study drug
  - c. Prolongation of QTc (Friderica formula) interval  $> 480$  ms
  - d. Cardiac arrhythmia requiring medical treatment for cardiovascular impairment

11. Bleeding or thrombotic disorders or use of anticoagulants requiring therapeutic INR monitoring, eg, warfarin or similar agents. Treatment with low molecular weight heparin is permitted.
12. Active hemoptysis (bright red blood of at least 0.5 teaspoon or 2.5 mL) within 3 weeks of the first dose of study drug
13. Active infections that require systemic treatment
14. Human immunodeficiency virus (HIV) positive
15. Positive serology for Hepatitis B (HB) defined as a positive test for HBsAg. In addition, if negative for HBsAg but HBcAb and/or HBsAb positive, an HBV DNA test will be performed and if positive the subject will be excluded
16. A history of interstitial pneumonia with clinical manifestation or as confirmed by means of diagnostic imaging
17. Medical need for the continued use of potent or moderate inhibitors of CYP3A or P-gp, or potent or moderate inducer of CYP3A. Subjects are eligible if 7 days or longer have passed since the last use of such agents prior to the first dose of study drug.
18. Known intolerance to lenvatinib (or any of the excipients) or known hypersensitivity to everolimus (or any of the excipients) or rapamycins (sirolimus, temsirolimus and so on)
19. Alcohol or drug dependency or abuse, inability to comply with every aspects of the study protocol, or any physical or mental conditions that in the opinion of the investigators would preclude the subject's participation in the study
20. Females who are pregnant or breastfeeding (not eligible even she discontinues breastfeeding)
21. Any medical or other condition which, in the opinion of the investigator, would preclude participation in a clinical trial

### 9.3.3 Removal of Subjects from Therapy or Assessment

The investigator may discontinue treating a subject with study treatment or withdraw the subject from the study at any time for safety or administrative reasons. The subject may decide to discontinue study treatment or withdraw from the study at any time for any reason. The reason for discontinuation will be documented. If a subject discontinues study treatment, the subject will enter the Follow-up Period and complete protocol-specified off-treatment visits, procedures, and survival follow-up unless the subject withdraws consent.

The investigator should confirm whether a subject will withdraw from study treatment but agree to continue protocol-specified, off-treatment study visits, procedures, and survival follow-up, or whether the subject will withdraw consent. If a subject withdraws consent, the date will be documented in the source documents. The Subject Disposition CRF page will be completed indicating the primary reason for discontinuation and all other reason(s) contributing to the subject's discontinuation from treatment. In addition, the date of last dose of study drug(s) will be recorded on the CRF.

### 9.3.3.1 Discontinuation for Individual Subjects

1. Subjects will continue to receive study treatment unless: Subject wishes to discontinue the treatment or withdraw the consent
2. Significant violation in eligibility is confirmed after subject's study enrollment
3. Subject experiences an AE that is difficult to continue the study treatment, in the opinion of investigator or subinvestigator.
4. Subject is pregnant
5. Disease progression is observed. Subject will be able to continue study treatment if investigator or subinvestigator judges that the clinical benefit will outweigh.
6. Investigator or subinvestigator's decision to discontinue the treatment.

When subject withdraws from lenvatinib, everolimus will also be discontinued. Discontinuation assessments will be performed within 7 days and the final observation will be conducted on 30 days (+7 days) after the final dose of study treatment.

## 9.4 Treatments

Lenvatinib and everolimus will be orally administered to subjects once daily in a 28-day cycle. During Cycle 1, subjects will receive the drugs in the morning after fasting with no food consumption for one hour postdose. In Cycle 2 and onward, subjects will receive study drug either fasted condition or at after meal and maintain the same dosing condition once it is decided.

Lenvatinib will be administered at starting dose of 18 mg in combination with everolimus at starting dose of 5 mg.

### 9.4.1 Drug interruption and dose reduction

1. Cycle 1
  - a. If DLT occurs:

Lenvatinib and everolimus must be interrupted immediately. Treatment may be resumed in Cycle 2 at one lower dose level of lenvatinib and/or reduction of everolimus to 5 mg every other day or discontinuation of everolimus if toxicity is resolved to Grade 0–1 or baseline and investigator or subinvestigator decides to continue the study.
  - b. No DLT:

Lenvatinib and everolimus will be interrupted if judged to be clinically needed by investigators, and may be resumed at the same dose level at appropriate timing. No dose reduction is permitted.
2. Cycle 2 and onward

Dose reduction and interruption for subjects who experience lenvatinib and/or everolimus related toxicity will follow the instructions shown in Table 2. Dose

reductions occur in succession based on the previous dose level (14, 10, 8 mg/day). Any dose modification must be discussed with the sponsor when toxicities occur at the dose of 8 mg/day. Once the dose has been reduced, it cannot be increased at a later date. For management of hypertension and interstitial lung disease, refer to instructions '9.4.2 Management of Hypertension' and '9.4.7 Management of interstitial lung disease' before consulting the table below, as appropriate.

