Subjects will discontinue study treatment at the time of disease progression, development of unacceptable toxicity, withdrawal of consent, or qualifies any of the criteria described in '9.3.3.1 Discontinuation for Individual Subjects'. The discontinuation assessments will occur within 7 days and off-treatment visit on 30th day after the final dose of study treatment.

DLT is defined as toxicity related to this combination therapy as indicated below.

Table 1. Dose Limiting Toxicities (DLT)

Toxicity Category	Toxicity/CTCAE Grade
Hematologic	
 
• Grade 4 neutropenia lasting >7 days
 
• Grade 3 febrile neutropenia (axillary temperature <math>\geq 38.5^{\circ}\text{C}</math> and neutrophils <math>< 1 \times 10^3/\mu\text{L}</math> (<math>< 1000/\text{mm}^3</math>))
 
• Grade <math>\geq 3</math> thrombocytopenia lasting >7 days or requiring blood transfusion
 

Non-hematologic toxicity	
 
• Grade 3 non-hematologic toxicities lasting >7 days except for the following: 
 
➢ Clinically insignificant or transient abnormal laboratory findings
 
➢ Able to be controlled by maximal supportive therapy
 
 Grade <math>\geq 3</math> hyperamylasemia or hyperlipasemia without clinical or other evidence of pancreatitis are not regarded as a DLT. 
 
• Grade <math>\geq 3</math> Nausea, vomiting or diarrhea lasting >7 days despite maximal medical therapy
 
• Hypertension uncontrolled by medication
 
• Any thromboembolic event including cerebrovascular hemorrhage/events
 

Medication compliance	
 
• Failure to administer <math>\geq 75\%</math> of the planned dosage of lenvatinib or everolimus as a result of treatment related toxicity
 

Overall study design is presented below.

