**Table 2. Dose Reduction and Interruption Instructions for Lenvatinib/Everolimus Combination Treatmenta**

Lenvatinib/Everolimus Treatment-Related Toxicity b,c,d	During Therapy	Adjusted Dose
Grade 1 or Tolerable Grade 2b	Continue treatment	No change
Intolerable Grade 2b or Grade 3	Interrupt lenvatinib and everolimus until resolved to Grade 0–1 or baseline	Investigators will decide the probability of the event being related to one or both drugs as to whether dose modification of one or both drugs is required.  Dose reduction lenvatinib by one level and/or reduce everolimus to 5 mg every other day or discontinuation of everolimus and resume the treatment.
Grade 4c	Discontinue study treatment	

a: An interruption of study treatment for more than 28 days due to treatment-related toxicity will require a discussion with the sponsor before treatment can be resumed.

b: Tolerability Grade 2 toxicities will be judged by the study investigators to be intolerable.

c: Excluding laboratory abnormalities judged to be non-life-threatening, in which case manage as Grade 3.

d: Initiate optimal medical management for nausea, vomiting, diarrhea prior to any treatment interruption, or dose reduction. If uncontrolled, the management will be followed by this guideline.

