#### 9.4.5 Management of Thromboembolic Events

Subjects should be advised to pay attention to the symptoms suggestive of venous thromboembolic events, which include acute onset of dyspnea, chest pain, cough, hemoptysis, tachypnea, tachycardia, cyanosis, DVT signs including lower-extremity swelling, redness and warmth to touch or tenderness. In case any of these signs or symptoms appears, subjects should be instructed to report such signs and symptoms promptly to the treating physician. If a thromboembolic event is confirmed, instructions contained in Table 2 of the protocol should be followed, "Study Treatment Dose Reduction and Interruption Instructions." Appropriate supportive care should be provided together with close monitoring. If a subject experiences life-threatening (Grade 4) thromboembolic reactions, including pulmonary embolism, both lenvatinib and everolimus must be discontinued.

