- Severe (Grade 3) condition: Interrupt study treatment (lenvatinib and everolimus) and consider using adrenal cortical hormone. If it is resolved to Grade 0-1 or baseline, resume study treatment with lenvatinib alone after resolving to Grade 0-1 or baseline according to his/her clinical condition. Investigator will make a decision on whether the subject can resume the study treatment and if so, as well as the dose level. Everolimus must not be concomitantly administered.
- If a subject experiences life-threatening (Grade 4) event, both lenvatinib and everolimus must be discontinued.

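### In Cycle 1, Protocol 9.4.1 permits treatment to resume after a Grade 4 event that 9.4.2, 9.4.5 or 9.4.7 says must end it, and the reach of Table 2 in Cycle 1 is unclear

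*Protocol*

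**What the plan says.** **Cycle 1 rules.** Protocol 9.4.1 item 1 has two branches, both repeated in the synopsis.

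- Item 1a (a DLT has occurred): both drugs are interrupted at once. Then "Treatment may be resumed in Cycle 2 at one lower dose level of lenvatinib", and/or with everolimus cut to 5 mg on alternate days, or with everolimus dropped. Two conditions apply: the toxicity has settled to Grade 1 or below or to its baseline level, and the "investigator or subinvestigator decides to continue the study".
- Item 1b (no DLT): the drugs are interrupted if clinically needed and "may be resumed at the same dose level at appropriate timing. No dose reduction is permitted".

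**Grade 4 rules elsewhere.**

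- 9.4.2 item 7: both drugs are discontinued for Grade 4 hypertension.
- 9.4.5: "If a subject experiences life-threatening (Grade 4) thromboembolic reactions, including pulmonary embolism, both lenvatinib and everolimus must be discontinued".
- 9.4.7, on interstitial lung disease: "If a subject experiences life-threatening (Grade 4) event, both lenvatinib and everolimus must be discontinued".
- Table 2, Grade 4 row: "Discontinue study treatment". Footnote c moves laboratory abnormalities judged not to threaten life to the Grade 3 row.

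**What counts as a DLT.** Table 1 in Protocol 9.1 lists, among treatment-related toxicities, "Any thromboembolic event including cerebrovascular hemorrhage/events", with no grade attached.

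**The concern.** The grade of the event is not a condition in either branch of 9.4.1 item 1. A life-threatening event in Cycle 1 can therefore qualify for renewed treatment under 9.4.1 while another section requires treatment to end. An investigator who resumes after such an event follows one section and breaches another.

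Two things depend on which section is opened. The first is the safety of a subject who has just had a life-threatening event, in a study that Protocol 7.5 describes as the first use of this combination in Japan. The second is where the subject is counted: SAP 5.6.2 tabulates events leading to discontinuation, to dose reduction and to dose interruption separately. The tolerability review in Protocol 9.1 also weighs toxicities up to Cycle 2 that interruption or reduction cannot manage, so how such an event was handled is part of what that review looks at.

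**Working it through.** The plan gives no figure on this point, so the check sets the passages side by side.

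| Grade 4 event in Cycle 1 | Branch of 9.4.1 item 1 | What that branch permits | What another section says, without a cycle limit |
|---|---|---|---|
| Thromboembolic, treatment-related | 1a, since Table 1 makes it a DLT at any grade | Restart in Cycle 2 on a reduced regimen | 9.4.5: both drugs stopped |
| Hypertension | 1a if medication does not control it; otherwise the branch turns on DLT status | Restart, reduced (1a) or at the same dose (1b) | 9.4.2 item 7: both drugs stopped |
| Interstitial lung disease | 1a or 1b, by DLT status | Restart, reduced (1a) or at the same dose (1b) | 9.4.7: both drugs stopped |
| Other toxicity | 1a or 1b, by DLT status | Restart, reduced (1a) or at the same dose (1b) | Table 2 stops treatment, subject to footnote c, if it applies in Cycle 1 |

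**Step 1, the clearest case.** Take a treatment-related Grade 4 pulmonary embolism in Cycle 1. It is a DLT under Table 1 without any judgement on grade or duration. Item 1a allows treatment in Cycle 2 once it has settled; 9.4.5 does not.

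**Step 2, the branch is not always certain.** The general non-hematologic line of Table 1 names Grade 3 only, while 9.4.11 item 3 speaks of Grade 3 or 4. So it is not settled whether some Grade 4 non-hematologic events go to 1a or 1b. Grade 4 neutropenia is a DLT only beyond 7 days, so shorter episodes go to 1b.

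**Step 3, does Table 2 apply in Cycle 1?** Section 9.4.1 and the synopsis introduce it only under the item for Cycle 2 and later. The table itself carries no cycle limit, and seven sections (9.4.3 to 9.4.6 and 9.4.8 to 9.4.10) send the reader to it without one. The answer depends on the section from which the reader arrives.

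**Step 4, is there an order of precedence?** The only such clause asks sites to consult 9.4.2 and 9.4.7 before the table. It sits under the item for Cycle 2 and later, and it does not name 9.4.5.

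**Step 5, could the event-specific sections be meant only for later cycles?** The text does not say so. Section 9.4.2 begins with checks at study entry and before Cycle 1, and sets monitoring for the Treatment Period, which 9.1.1.1 defines to include Cycle 1.

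**Step 6, effect on the tables.** The same embolism is counted under discontinuation of both drugs if 9.4.5 is followed. Under 1a it is counted under interruption and, on restart, under a reduction of one or both drugs or discontinuation of everolimus alone. With the planned 6 to 12 subjects (Protocol 9.3), one subject is 1/12 = 8.3% to 1/6 = 16.7% of a table.

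**The case against.** The strongest reply is that nothing in 9.4.1 tells a site to re-treat. Resumption is allowed, not required. It depends on recovery and, under 1a, on the investigator's decision, and 9.3.3.1 lets the investigator stop treatment at any time. A specific requirement is naturally read as limiting a general permission. This stands in part: a site that stops treatment complies with every passage. A reader might infer that the sections give directly opposing instructions, and that goes too far. What survives is that 9.4.1 permits something the three sections forbid. No text says that they prevail in Cycle 1, and 9.4.1 item 1 could equally be taken as the specific rule, since it is the one written for that cycle.

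A reader might also infer that Table 2 binds only from Cycle 2, so that all other Grade 4 toxicities are handled more permissively in Cycle 1. The documents do not support that, given the table's own silence on cycle and the seven unrestricted references to it. The fair statement is that its reach is unclear.

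The non-DLT branch is also narrower than it looks. Missing more than 25% of planned dosage through treatment-related toxicity is itself a DLT. With 28 daily doses, 0.75 × 28 = 21, so more than 7 missed doses takes the subject to 1a. Footnote c further removes from the Grade 4 row laboratory abnormalities that do not threaten life. Both points stand, and they leave mainly short-lived events in 1b.

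Finally, a reader might infer that the discrepancy changes the DLT rate behind the one-third criterion in Protocol 9.1. For an event that is already a DLT it does not: the subject is counted in Cycle 1 whether or not treatment resumes in Cycle 2. For a 1b event the only link would be the missed-dose criterion just described. The documents do not work through that case, and the point does not rest on it.

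**Conclusion.** The inconsistency is real and limited. For three event types, Grade 4 hypertension, thromboembolic reactions and interstitial lung disease, 9.4.1 item 1 permits resumption after a Cycle 1 event where another section requires both drugs to end. Thromboembolism is the clearest, because a treatment-related event is always a DLT. For other Grade 4 toxicities the fault is ambiguity about whether Table 2 applies in Cycle 1, subject to footnote c.

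The consequences are for patient safety and for the discontinuation, reduction and interruption tables. They are not a shift in the Cycle 1 DLT count from resuming in Cycle 2. The 8.3% to 16.7% per subject assumes a denominator of 6 to 12 treated subjects. The documents give no expected frequency of Grade 4 events in Cycle 1 for this population, so the number of subjects affected cannot be estimated and may be none. The sponsor should correct this because the events are life-threatening and the correction is small.

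**What to change.** Reconcile 9.4.1 item 1, and the matching synopsis text on interruption and dose reduction, with 9.4.2 item 7, 9.4.5, 9.4.7 and Table 2. State which passage governs a Grade 4 event in Cycle 1, separately for events that are DLTs and events that are not. State also whether Table 2, with footnote c, applies in Cycle 1, and include 9.4.5 in any order of precedence. Which clinical rule should hold is for the sponsor to decide; this review takes no view.

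The cost is about one sentence in 9.4.1 and its counterpart in the synopsis. Because the text concerns subject safety, Protocol 11.1 would require the amendment to go to the authorities and the review boards. Sample size, data collection and the SAP tables need no change.

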**Table 2. Dose Reduction and Interruption Instructions for Lenvatinib/Everolimus Combination Treatmenta**

Lenvatinib/Everolimus Treatment-Related Toxicity b,c,d	During Therapy	Adjusted Dose
Grade 1 or Tolerable Grade 2b	Continue treatment	No change
Intolerable Grade 2b or Grade 3	Interrupt lenvatinib and everolimus until resolved to Grade 0–1 or baseline	Investigators will decide the probability of the event being related to one or both drugs as to whether dose modification of one or both drugs is required.  Dose reduction lenvatinib by one level and/or reduce everolimus to 5 mg every other day or discontinuation of everolimus and resume the treatment.
Grade 4c	Discontinue study treatment	

a: An interruption of study treatment for more than 28 days due to treatment-related toxicity will require a discussion with the sponsor before treatment can be resumed.

b: Tolerability Grade 2 toxicities will be judged by the study investigators to be intolerable.

c: Excluding laboratory abnormalities judged to be non-life-threatening, in which case manage as Grade 3.

d: Initiate optimal medical management for nausea, vomiting, diarrhea prior to any treatment interruption, or dose reduction. If uncontrolled, the management will be followed by this guideline.

### 9.4.2 Management of Hypertension

Hypertension is a recognized side effect of treatment with drugs inhibiting VEGF signaling. Early detection and effective management of hypertension are important to minimize the need for lenvatinib dose interruptions and reductions.

The following guideline should be followed for the management of hypertension:

1. Ensure that subjects have BP  $\leq$  150/90 mm Hg at the time of study entry
2. If known to be hypertensive, confirm that the subject has been on a stable dose of antihypertensive therapy for at least 1 week before Cycle 1/Day 1.
3. Antihypertensive agents should be started as soon as elevated BP (systolic BP  $\geq$  140 mm Hg or diastolic BP  $\geq$  90 mm Hg) is confirmed on two assessments a minimum of 30 minutes apart. One BP assessment is defined as the mean value of two measurements at least 5 minutes apart. The choice of antihypertensive treatment

should be individualized to the subject's clinical circumstances and follow standard medical practice.

4. For previously normotensive subjects, appropriate antihypertensive therapy should be started when systolic BP  $\geq$  140 mm Hg or diastolic BP  $\geq$  90 mm Hg is first observed on two assessments a minimum of 30 minutes apart. For those subjects already on antihypertensive medication, treatment modification may be necessary if hypertension persists. For subjects with hypertension and proteinuria, appropriate therapy, eg, angiotensin-converting enzyme inhibitor or angiotensin-II receptor antagonist is preferred.
5. Lenvatinib and everolimus should be withheld in any instance where a subject is at imminent risk to develop a hypertensive crisis or has significant risk factors for severe complications of uncontrolled hypertension (eg, BP  $\geq$  160/100 mm Hg, significant risk factors for cardiac disease, intracerebral hemorrhage, or other significant co-morbidities). Once the subject has been on the same hypertensive medications for at least 48 hours and the BP is controlled, lenvatinib should be resumed as described below.
6. The following guidelines should be followed for the management of systolic BP  $\geq$  160 mm Hg or diastolic BP  $\geq$  100 mm Hg confirmed on repeat measurements after 30 minutes:
  - Continue lenvatinib and everolimus, and institute antihypertensive therapy for subjects not already receiving antihypertensive medication
  - For the subjects already on antihypertensive medication, dose or medication choice should be modified per investigators judgment.
  - If systolic BP  $\geq$  160 mm Hg or diastolic BP  $\geq$  100 mm Hg persists despite maximal antihypertensive therapy, then lenvatinib and everolimus administrations should be interrupted and restarted at a dose of one level lower for lenvatinib only when systolic BP  $\leq$  150 mm Hg and diastolic BP  $\leq$  95 mm Hg and the subject has been on a stable dose of antihypertensive medication for at least 48 hours. Dose for everolimus will remain the same.
  - If systolic BP  $\geq$  160 mm Hg or diastolic BP  $\geq$  100 mm Hg recurs with the reduced dose of lenvatinib despite optimal management of hypertension with antihypertensive medications (either by dose increase or the addition of a different class of antihypertensive), then lenvatinib and everolimus administrations should be interrupted and restarted at a dose of another lower level for lenvatinib, only when systolic BP  $\leq$  150 mm Hg and diastolic BP  $\leq$  95 mm Hg and the subject has been on a stable dose of antihypertensive medication for at least 48 hours. Dose for everolimus will remain the same.
  - During the Treatment Period, both in the Randomization Phase and in the Extension Phase, subjects with systolic BP  $\geq$  160 mm Hg or diastolic BP  $\geq$  100 mm Hg must have their BP monitored every 2 weeks (on Day 15 or more frequently as clinical indicated) until systolic BP has been  $\leq$  150 mm Hg and diastolic BP has been  $\leq$  95 mm Hg for 3 consecutive months. If a repeat event of

systolic BP  $\geq$  160 mm Hg or diastolic BP  $\geq$  100 mm Hg occurs, the subject must resume the Day 15 evaluation until systolic BP has been  $\leq$  150 mm Hg and diastolic BP has been  $\leq$  95 mm Hg for 3 consecutive months.

7. If Grade 4 hypertension (life-threatening consequences) is observed, appropriate medical management will be introduced and lenvatinib and everolimus will be discontinued.

